## Trial schedule

### START HCQ block

Table 1-1

Visit	Screening evaluations and Visit 1	Visit 2	Email-/Phone-Visit	Visit 3	Email-/Phone-Visit	Visit 4
Action	„Start of baseline“	“End of baseline“ + Day 1 of treatment	Every 7 days at home	End of 1 st Tx period	Every 7 days at home	“End of trial”
Trial day	-28 to -3	1	7, 14, 21 (+/- 3)	28 (-4, +7)	35, 42, 49 (+/- 3)	56 (-4, +7)
Demographics (e.g. sex, age)	X					
Patient information, informed consent	X					
Previous (last 12 months) and concomitant diseases	X	X	X	X	X	X
Previous (last 3 months) and concomitant treatments	X	X	X	X	X	X
Inclusion/exclusion criteria	X	X 				
Pregnancy test K	X*			X		X
Randomization a	X					
Trial medication supply to patient		X		X		
History (cardiotoxicity, hypoglycaemia)	X	X		X		X
Physical examination	X	X		X		X
Vital signs (BP, pulse, temp) b	X	X		X		X
ECG i	X*			X		X
Ophthalmologic review j	X*					X
Lab c (GOT/GPT/Crea/Potassium/CK/gGT/LDH/BB/DIFF / HCQ drug level, blood glucose)	X*			X		X
pO 2 , pCO 2 (capillary)	X	X 		X 		X 
O 2 -sat e , in room air	X	X	X	X	X	X
Respiratory rate, in room air	X	X	X	X	X	X
Retractions	X	X	X	X	X	X
Coughing	X	X	X	X	X	X
Oxygen demand	X	X	X	X	X	X
Chest x-ray	X 			X 		

CONFIDENTIAL

Visit	Screening evaluations and Visit 1	Visit 2	Email-/Phone-Visit	Visit 3	Email-/Phone-Visit	Visit 4
Pulmonary hypertension (Echo) j	X*					
Quality-of-life i	X*			X		X
Health Economics h	X*			X		X
Weight for height b	X*	X		X		X
Clinical course of lung disease	X 	X 	X 	X 	X 	X 
Exacerbation o	X 	X 	X 	X 	X 	X 
Adverse events	X	X	X	X	X	X
Drug accountability				X		X
Additionally in children > 5 years						
Spirometry / Bodyplethysmography a	X	X		X		X
6 minute walking distance (meter) g	X	X		X		X
O 2 -saturation before and after 6MWT	X	X		X		X
Borg scale t	X	X		X		X
Additionally in ventilated patients m						
Oxygenation index (OI) n	X	X	X	X	X	X
Duration (h) of mechanical ventilation	X	X	X	X	X	X
NO (%), ECLS (VV/VA/ECLA/Flow/time since insertion)	X	X	X	X	X	X

X\* Tests must be done before first drug dosing

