h Health economics assessment with the use of a special questionnaire which has to be filled out by the parents or adult patients.

i Quality of Life assessment with the use of the questionnaire PedsQL for different age groups which has to be filled out by parents and/or patients

j For Electrocardiography (ECG), ophthalmological review and Echocardiography (Echo) please see Chapter 5. If a routine ophthalmological examination was done within 3 month before Visit 1, no additional ophthalmological exam is required.

k Pregnancy test only has to be performed in girls of childbearing age and only if sexual relations are known or probable. It is at the discretion and responsibility of the attending physician to decide, whether a pregnancy test is necessary or not. The pregnancy test can be performed in the urine or serum.

l The following parameter will also be assessed, if there is **oxygen demand**:

1. O2 via nasal cannula or via face mask: O2-Flow (l/min)
2. on high-flow nasal cannula: Flow air (l/min), O2-Flow (l/min), FiO2

m The following parameter will also be assessed on ventilation: ventilation method, duration of ventilation (hours/day/only for non-invasive ventilation), PEEP (cmH2O), PIP (cmH2O), FiO2, Ti (sec), MPAW (cmH2O) and Oxygenation Index (OI);  
In addition, if patients on the heart lung machine (e.g. NO (%), ECLS (VV/VA/ECLA), Flow/time since insertion) will be documented descriptively.

n Calculation of Oxygenation Index (OI): OI = (FiO2 \* MPAW)/PaO2

with MPAW = ((frequency \* inspiration time)/60) \* ((inspiratory pressure (PIP) – PEEP) + PEEP)); If PaO2 is not available, PcapO2 can be used.)

o Start date, End date, Patient returned to baseline function? Y/N

1. Increase in respiratory rate? Y/N/not done.

2. Increase or development of dyspnea ? Y/N

3. Newly developing or increased abnormalities on chest imaging ? Y/N/not done

4. Onset/increase of oxygen demand to attain the individual baseline saturation ? Y/N

5. Need for an additional level of ventilatory support (in addition to oxygen) ? Y/N

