## 8 STATISTICS

Details of the statistical analysis of the data collected in this trial will be documented in a Statistical Analysis Plan (SAP) that will be generated by IZKS Mainz and finalized before closing the data base and prior to breaking the blind. The SAP is based on the protocol including all amendments. The document may modify the plans outlined in this protocol; however any major modifications of the primary outcome definition and/or its analysis will also be reflected in a protocol amendment. Any deviation from the original statistical plan must be described and justified in the final report. The statistical analysis will be conducted by means of SAS®.

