#### 8.3.1 Definition and analysis of primary outcome

The oxygenation of the patient is the primary outcome variable. The primary outcome will be assessed as the response rate of oxygenation to the intervention. As the patient's respiratory condition can vary over a broad range, may necessitate variable external support, and as these changes may occur over relatively short time periods, it is necessary to take all this into consideration when assessing oxygenation. Therefore we defined the parameters to be measured depending on the patient's condition to define a responder (Table 3.8-1). The majority of children included into the study are expected to be on supplemental oxygen or in room air. In these subjects oxygen saturation in room air will be assessed (for assessments please see 3.2). However to include the broad continuum of respiratory support possible in individual patients, an approach was chosen accommodating that need. Responses to treatment judged as significant were defined depending on Patient's condition. How and when to assess the variables is further detailed in the study protocol.

Oxygenation, the primary outcome parameter, was chosen as a dichotomous variable (response yes or no). Its components, i.e. O2-saturation and respiratory rate, are also used continuously in a descriptive manner as secondary outcome variables.

Tab 3.8-1: Definition of responders to treatment depending on Patient's condition

Patient's condition	Measured parameters	Specific metric	Definition of significant change or responder to the initiation of HCQ	Definition of significant change or responder to the withdrawal of HCQ	Method of aggregation
In room air	In room air O2 Sat (mean value) Respir rate (mean value)	Change from baseline	Increase $\geq 5\%$ in O2 Sat, or Decrease in resp. rate $\geq 20\%$	Decrease $\geq 5\%$ in O2 Sat, or Increase in resp. rate $\geq 20\%$	Proportion of responders
On O2-supplement	In room air O2 Sat (mean value) Respir rate (mean value)	Change from baseline	Increase $\geq 5\%$ in O2 Sat or Decrease in resp. rate $\geq 20\%$ or Support no more needed	Decrease $\geq 5\%$ in O2 Sat, or Increase in resp. rate $\geq 20\%$ or Support newly needed	Proportion of responders
On high-flow nasal cannula	O2-flow, air-flow	Change from baseline	Decrease $\geq 20\%$ or Support no more needed	Increase $\geq 20\%$ or Support newly needed	Proportion of responders

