4.1 Demographics and Baseline Characteristics

Demographics

Birth date (not analysed)

Gender

Age (calculated)

Nationality

Baseline Characteristics

Concomitant diseases (in the year before screening / current)

*Physical examination (without finding yes/no, several body systems
normal/abnormal)

*Vital signs (height (cm), weight (kg), heart rate (b/min), blood pressure
systolic (mmHg), blood pressure diastolic (mmHg), BMI (calculated),
temperature, cardiotoxicity, hypoglycaemia)

*O2-Saturation (not done / method, O2-Saturation % on room air, O2-Saturation %
and O2-flow (l/min) on oxygen via nasal cannula or face mask)

O2-Saturation – air challenge (not done for 5 minutes, O2-Saturation %, unable to tolerate RA challenge time to saturation of 80%)
O2-Saturation – on high-flow nasal cannula (O2-Satuation %, Flow air, Flow O2)
O2-Saturation – on non-invasive ventilation (O2-Saturation %, PEEP, PIP, Respiratory rate not done)
O2-Saturation – on invasive ventilation (O2-Saturation %, PEEP, PIP, Respiratory rate not done)
O2- saturation - on HFO (O2-saturation %, frequency FHFO, MAP, Amplitude VTHFO)
O2-saturation – on ECMO (O2-saturation %)

****Standard exercise testing (6min-walk not done/not completed/completed, reason for not done) – distance, oxygen saturation, heart rate, Borg-scale (0=nothing at all, ..., 10=very, very severe (max.) at rest and immediately after exercise), if on oxygen: oxygen supplement and flow rate, if test was discontinued: reason and discontinued after xy seconds)**

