4.2 Primary Variable

START HCQ block and STOP HCQ block

The primary variable is the response rate measured by the oxygen saturation in room air.

START HCQ block

Relative change from trial day 1, i.e. Visit 2, through day 28, i.e. Visit 3, change from active compound compared to change from placebo

STOP HCQ block

Relative change from trial day 1, i.e. Visit 2, through day 84, i.e. Visit 5: change from active compound compared to change from placebo

A) Non-ventilated patients in room air or on O2-supplement

Oxygen saturation in room air

Assessment:

1) If not on O2:

(after 5 min at rest room air, then measure twice over 1 minute each, at least 1 min apart)

** O2 Sat (mean value)*

* Respiratory rate (mean value)

2) If on O2: BEFORE withdrawal:

(after 5 min at rest with steady state O2 supplement, then measured over 1 minute)

* O2 Flow

* O2 Sat (mean value)

* Respiratory rate

Then withdraw O2:

Steady state O2 Sat in air obtained. Steady state minimum SpO2 should be at least 30 seconds without change. Then measured twice over 1 minute each, at least 1 min apart.

If falls to SpO2<80% place back in oxygen and note as <80%.

* O2 Sat (mean value)

* Respiratory rate (mean value)

B) If on high-flow nasal prongs:

O2-flow and air-flow

C) Ventilated patients:

Oxygenation index (OI)

OI = (FiO2 * MPAW) / PaO2

with

FiO2 = Fraction of inspired oxygen

MPAW = Mean airway pressure (= ((frequency * inspiration time)/60) * ((inspiratory pressure (PIP) – PEEP) + PEEP)))

PaO2 = Partial pressure of oxygen in arterial blood

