6.6 Primary Analysis

The variable assessing the primary outcome is the response rate measured by the oxygen saturation in room air.

START HCQ block

Relative change from trial day 1 (Visit 2) to day 28 (Visit 3) and day 56 (Visit 4) and from day 28 to day 56 change from active compound compared to change from placebo

STOP HCQ block

Relative change from trial day 1, i.e. Visit 2, through day 84, i.e. Visit 5: change from active compound compared to change from placebo

Both blocks separately

a) A difference between the changes in placebo and active phases is considered significant as described in the table below.

Patient's condition	Measured parameter	Definition of significant change or responder
Stable in room air or on	SpO2 in room air	Increase $\geq 5\%$

O2-supplement		
On high-flow nasal cannula	O2-flow, air-flow	Decrease $\geq 20\%$ or support not needed any more
Ventilated	Oxygenation index	Decrease $\geq 20\%$ or support not needed any more
On ECMO		Decrease $\geq 20\%$ or support not needed any more

The analysis will be done first by discarding the information on the patient's condition. Descriptive analyses will be done overall and for all patients conditions separately.

b) Patients are defined as responder as described in the table above. The numbers of responders are counted and compared by Fisher's exact test as well as logistic regression models with factors for treatment group and age group.

The following SAS code can be used:

```
PROC LOGISTIC DATA=indata;
  CLASS treatment age_gr;
  MODEL responder_YN = treatment age_group treatment*age_group;
RUN;
```

Both blocks together

Not applicable. There were too few patients in both blocks.

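### The printed mean airway pressure formula cancels PEEP, so a ventilated patient's 20% oxygenation index response can be misclassified when ventilator settings change

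*SAP*

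**What the plan says.** For ventilated patients the primary measure is OI = FiO2 × MPAW / PaO2. SAP 4.2 C defines MPAW as "frequency * inspiration time)/60) * ((inspiratory pressure (PIP) – PEEP) + PEEP". Protocol Tab 3.3-1 has the same expression, and footnote n to the trial schedule has "frequency \* inspiration time)/60) \* ((inspiratory pressure (P IP ) – PEEP) + PEEP".

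The schedule rows for OI in Protocol Tables 1-1 and 1-2 carry the marker for that footnote ("Oxygenation index (OI) n"), so a site following the schedule is led to the formula. Footnote m, however, lists MPAW among the parameters recorded on ventilation, beside inspiration time and OI ("T i (sec), M PAW (cmH 2 O) and Oxygenation Index (OI"), without giving its source. SAP 4.1 lists a mean airway pressure directly for one mode only: "on HFO (O2-saturation %, frequency FHFO, MAP, Amplitude VTHFO". Its entries for invasive and non-invasive ventilation show PEEP, PIP and respiratory rate, but no MPAW and no inspiration time.

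Response for ventilated patients is an OI fall of at least 20% "or support not needed any more" (SAP 6.6). Protocol Tab 3.8-1 has the same rule for initiation of HCQ. For withdrawal it uses a rise of at least 20%, or support newly needed. SAP 6.6 analyses all patients together first, regardless of respiratory condition.

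**The concern.** Subtracting PEEP and adding it back inside the same bracket does nothing. The expression only makes sense if the final PEEP term stands outside the product. As printed, a change in PEEP leaves OI untouched, while changes in frequency, inspiration time or PIP move it too much in relative terms.

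This matters because OI decides the primary outcome class in these patients, and those classes enter the pooled responder comparison. The absolute level of OI is not the issue, since response uses relative change from baseline. The issue is whether the relative change is right when settings differ between the two visits.

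**Working it through.** The documents give no numerical example to reproduce, so the check is of the algebra, followed by illustrations. All ventilator settings below are assumed.

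**1. Grouping.** In all three places the two brackets opened before the inspiratory pressure term close only after the added PEEP. Tab 3.3-1 has balanced brackets (six open, six close). SAP 4.2 has one surplus closing bracket (six and seven), as does footnote n (five and six), but the surplus comes after this group and does not release PEEP from the product. PDF extraction therefore does not explain the error.

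**2. Algebra.** Let d = f × Ti/60, the fraction of the cycle spent in inspiration.

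- Printed: d × ((PIP − PEEP) + PEEP) = d × PIP.
- Time average of a square pressure wave: d × PIP + (1 − d) × PEEP = d × (PIP − PEEP) + PEEP.
- Difference: (1 − d) × PEEP.
- The printed value is below PEEP whenever d < PEEP/PIP. No average of pressures lying between PEEP and PIP can be.

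**3. Level.** Take f = 40/min, Ti = 0.5 s, PIP = 20, PEEP = 8 cmH2O, so d = 40 × 0.5/60 = 0.333.

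- Printed: 0.333 × 20 = 6.67, which is below PEEP.
- Corrected: 0.333 × 12 + 8 = 12.0.
- Shortfall: 5.33 = 0.667 × 8.

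**4. When the relative change is wrong.** Printed/corrected = 1/(1 + (1/d − 1) × PEEP/PIP). The two forms give the same relative change if (1/d − 1) × PEEP/PIP is the same at both visits, and different ones otherwise.

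**5. Effect on the decrease rule.** The rule is met when (ratio of FiO2/PaO2) × (ratio of MPAW) ≤ 0.80. The cut-off for the FiO2/PaO2 ratio is thus 0.80 divided by the MPAW ratio, and the classes differ between the two cut-offs. OI changes in the table hold FiO2 and PaO2 constant.

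| Change from step 3 settings | MPAW printed | MPAW corrected | OI change, printed | OI change, corrected | FiO2/PaO2 change over which classes differ |
|---|---|---|---|---|---|
| PIP 20 to 16 | 5.33 | 10.67 | −20.0% | −11.1% | −10.0% to 0% |
| PEEP 8 to 4 | 6.67 | 9.33 | 0% | −22.2% | −20.0% to +2.9% |
| f 40 to 30 | 5.00 | 11.00 | −25.0% | −8.3% | −12.7% to +6.7% |
| PIP 20 to 16 and PEEP 8 to 6.4 | 5.33 | 9.60 | −20.0% | −20.0% | none |

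For PEEP 8 to 4, for example, the cut-offs are 0.80/1.000 = 0.800 and 0.80/0.7778 = 1.029.

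**6. Protocol increase rule for withdrawal.** With f, Ti and PIP as in step 3 and PEEP 5 to 8, printed MPAW stays at 6.67 (0%), while corrected MPAW goes from 10.0 to 12.0 (+20.0%, which meets the rule).

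**7. How often the forms disagree.** A simulation drew uniform values (f 20–50/min, Ti 0.4–0.7 s, PIP 14–28, PEEP 4–9) and let FiO2/PaO2 change by up to ±40%.

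| Variation in each setting between visits | Disagreement, decrease rule | Disagreement, increase rule |
|---|---|---|
| none | 0% | 0% |
| ±10% | 4.8% | 6.8% |
| ±20% | 10.0% | 10.0% |
| ±30% | 14.5% | 11.9% |

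These rates show the mechanism; they do not estimate trial data.

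**The case against.** The strongest reply is that this is a slip with an obvious intended meaning, and that nothing shows the formula was used. MPAW is listed as a recorded parameter in its own right. Footnote m does not list ventilator frequency, the first input to the formula. The SAP prescribes no central derivation, so a reading from the ventilator is quite possible. The corrected form is itself only a square-wave approximation, and the documents state no waveform.

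The examples also use sizeable single changes. From the same baseline, with FiO2 and PaO2 constant, PEEP 8 to 6 gives 0% against −11.1%, which is the same class; PEEP must fall to 4.4 before the classes part. Few patients may be affected: "The majority of children included into the study are expected to be on supplemental oxygen or in room air". The support criterion can also settle response without OI.

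All of this stands as a limit on the size of the problem. It does not remove it. The schedule sends sites to the printed formula, no source for MPAW is specified, and a site that followed the text would have calculated an OI blind to PEEP. An obvious intention does not protect values already calculated as written.

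**Conclusion.** The error is certain as algebra and identical in the protocol and the SAP. Its effect on the data is conditional. Where MPAW was calculated as printed and settings changed so that (1/d − 1) × PEEP/PIP changed, the 20% class can be wrong in either direction. There is no effect if settings were unchanged, if MPAW was read from the ventilator, or if response was met through the support criterion. The formula is the same in both blinded arms, so this is possible misclassification and not a known bias between arms.

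The documents give no number of ventilated patients, so the effect on the overall response rate cannot be quantified; it is probably small. For scale only: 80 planned subjects split equally over two blocks and two arms is 80/4 = 20 per arm per block, so one misclassified patient would shift an arm's response rate by 1/20 = 5 percentage points. The point should be corrected before analysis, but it does not undermine the trial.

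**What to change.** - In SAP 4.2 C, Protocol Tab 3.3-1 and schedule footnote n, write MPAW = ((frequency × Ti)/60) × (PIP − PEEP) + PEEP, labelled as a square-wave approximation.
- Add one SAP sentence on the source: the ventilator-read MPAW where it is available at both baseline and follow-up, otherwise the corrected formula at both visits, so that the source is the same within a patient.
- Before unblinding, establish how each recorded MPAW and OI was obtained. SAP 6.6 already speaks in the past tense of too few patients in both blocks, which suggests that data exist, so correcting the text alone may not be enough.
- Recompute values derived from the printed formula where the inputs exist. Do not fall back on a recorded MPAW unless it is confirmed as a ventilator reading. List the patients for whom neither is possible.

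The cost is one bracket in three places, one sentence, and a provenance check limited to ventilated patients. Some OI values may prove unrecoverable, because frequency or inspiration time may not have been captured. Two of the corrections are in the protocol, so the sponsor should check them against its own rule that "any major modifications of the primary outcome definition and/or its analysis will also be reflected in a protocol amendment" (Protocol 8).

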4.2.1 Efficacy

The following variables will be investigated:

- Oxygen saturation (O2-sat, in room air) (only absolute, as relative already primary outcome) assessed at every visit (not web/tele feedback)
- Respiratory rate (RR, in room air) (relative and absolute) assessed at every visit and every web/tele feedback
- Retractions (yes/no) assessed at every visit and every web/tele feedback
- Coughing last 24 h (yes/no) assessed at every visit and every web/tele feedback
- Oxygen requirement assessed at every visit and every web/tele feedback
- pO2, pCO2 (capillary, in room air)
- Chest x-ray scoring for chILD assessed at screening and visit 3 (START HCQ Block) and visit 5 (STOP HCQ Block)
- Overall survival
- If > 5y old
 - FEV1 % predicted (recorded in L)
 - FVC % predicted (recorded in L)
 - reference values according to the GLI 2012 lung function regression equations
 - 6 minutes walking distance (meter)
 - O2-saturation before and after 6MWT
 - Borg scale
- If ventilated:
 - Duration (h) of mechanical ventilation
 - NO (%), ECMO yes/no, if yes VA/VV, double lumen vs. single lumen, Flow-rate.

4.2.2 *Safety/Tolerability*

Adverse events, clinical laboratory values (GOT, Creatinine, gGT, blood count, differential, LDH, BNP, steady state drug level), ECG, ophthalmologic review

Adverse events will be documented during the study at each visit (exemption: START HCQ between Visits 1 and 2. However, occurring AEs between those visits are not treatment emergent).

Laboratory data will be assessed at screening, visit 3 and visit 4 in the START HCQ Block and at screening, visit 3, 4 and visit 5 and EDTA additionally at visit 6 in the STOP HCQ Block.

Vital signs (respiratory rate, height, weight, BMI, heart rate, blood pressure (systolic and diastolic), temperature, hypoglycaemia (yes/no), appropriate observation of blood glucose levels (yes/no), cardiotoxicity (yes/no), appropriate ECG (yes/no)) will be assessed at screening, and every following visit (not web/tele feedback).

A physical examination will be done at the same visits.

Symptoms and clinical course of treatment will be documented at the same time points as the physical examination is performed and at telephone contact visit.

4.2.3 *Quality of Life (Peds QL)*

Not applicable.

4.2.4 *Health Economics*

Not applicable.

5 Treatment of Missing Values and Outliers

5.1 *Missing Values*

No substitution of missing values is planned.

5.2 *Outliers*

There will be no methods employed for detecting outliers.

6 Statistical Analyses

The default summary statistics for quantitative variables will be the number of observations (n), mean, standard deviation (SD), median, first quartile (Q1), third quartile (Q3), minimum and maximum for those patients with data available.

For qualitative variables, the number (n) and percentage (%) of patients with non-missing data per category will be the default summary presentation. If appropriate, the number of missing values will be displayed as a “Missing” category.

A value will be considered missing if a patient attends the visit (visit date is available) but no value is documented.

All variables will be displayed by treatment group and with a total column.

Listings of all AE data available will be provided only.

6.1 *Patient Disposition*

The following patient disposition variables will be presented by numbers and percentages:

- Informed consent given to study participation / study treatment
- Inclusion and exclusion criteria

- Size of analysis populations (enrolled, ITT, safety)
- Study completion according to protocol
- Reasons for premature discontinuation of study treatment
- Type of major protocol violation

Protocol deviations which are documented in the CRF will be listed additionally.

